## ABBREVIATIONS

Abbreviation	Definition
BSWH	Baylor Scott & White Health
CI	Confidence interval
COVID	Coronavirus disease
CP	Convalescent plasma
DHTR	Delayed hemolytic transfusion reaction
DSTR	Delayed serologic transfusion reaction
EHR	Electronic Health Records
EUA	Emergency use authorization
FDA	Food and Drug Administration
HIV	Human immunodeficiency virus
HR	Hazard ratio
ICU	Intensive care unit
ISBT	International Society of Blood Transfusion
ITT	Intent-to-treat
PTP	Post transfusion purpura
RCT	Randomized controlled trial
RT-PCR	Real-Time Polymerase chain reaction
SARS-CoV-2	Severe Acute Respiratory Syndrome Coronavirus 2
TACO	Transfusion associated circulatory overload
TAD	Transfusion-associated dyspnea
TRALI	Transfusion-related acute lung injury
TAGVHD	Transfusion-associated graft vs. host disease

## I. INTRODUCTION

The US Food and Drug Administration (FDA) authorized compassionate use of convalescent plasma for seriously ill patients infected with SARS-CoV-2 on March 25, 2020. Under the emergency use authorization (EUA), FDA expanded the use for treatment outside the scope of a trial. Although randomized controlled trials (RCTs) provide robust data to assess the efficacy and immune response of the intervention for COVID-19, complete data may not be available during critical periods in the current pandemic. While waiting for efficacy and safety data from ongoing clinical trials, inference gleaned from observational studies using secondary data (real-world data), e.g., electronic health records (EHRs) in an observational study, may provide more timely information in real-world clinical practice.

The goal of this study is to assess safety and effectiveness of anti-SARS-CoV-2 plasma in patients with coronavirus disease 2019 (COVID-19).

## II. OBJECTIVES

### A. PRIMARY OBJECTIVES

- (i) To estimate the relative risk of effectiveness outcomes of interest in laboratory confirmed COVID-19 patients who received convalescent plasma compared with COVID-19 patients who did not receive convalescent plasma.
- (ii) To describe safety outcomes of interest in laboratory confirmed COVID-19 patients who received convalescent plasma compared with COVID-19 patients who did not receive convalescent plasma.

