**Figure 1. Schematic diagram for retrospective cohort study with risk-set sampling for convalescent plasma exposure**

CP= convalescent plasma

\* Hospital admission includes the earliest encounters at emergency or inpatient departments around COVID-19 confirmation within  $\pm 14$  days.

† The earliest possible date is July 1st, 2020.

Step-by-step risk-set sampling with replacement for the retrospective cohort design to account for confounding and to strategize EHR abstraction at BSWH:

1. Identify patients hospitalized with laboratory-confirmed COVID-19 (Source population)

The study population will be patients with laboratory-confirmed COVID-19 (i.e., RT-PCR test results recorded by the BSWH laboratory informatics systems and/or the EHR system) and received or matched to a patient who received convalescent plasma from July 1st to September 28th. Patients must have at least 28 days of observation opportunity from the date of data pull to the index date (reverse order). Patients cannot have been previously admitted into hospitals due to RT-PCR laboratory confirmed COVID-19.

2. Identify patients who received convalescent plasma (Exposed group)

Blood bank records will be scanned to identify patients who had at least one order to transfuse COVID-19 convalescent plasma using the International Society of Blood Transfusion (ISBT) 128 codes (Appendix 1). The order will be linked to the administration record of the plasma to determine the date and time the product was given.

3. Risk-set sampling and matching variables (Unexposed group)

For each patient who received a first dose of convalescent plasma, we will sample from the source population who did not receive convalescent plasma (Unexposed group) at the same calendar time ( $\pm 2$  days) and match on the following variables. One patient could be sampled at maximum twice; first sampled into the unexposed group and later sampled into the exposed group due to initiation of convalescent plasma transfusion during follow-up.

- Calendar date around the index date within  $\pm 2$  days: Risk-set sampling to match exposed and unexposed patients will account for this factor
- Age ( $\pm 5$  years)
- Sex (female, male)
- Days from hospital admission to the index date

4. Propensity score matching and baseline covariates

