### Study Outcomes

- Safety

Safety events related to plasma transfusion were selected from the Centers for Disease Control and Prevention (CDC) National Healthcare Safety Network (NHSN) Biovigilance Component Hemovigilance Module Surveillance Protocol.a The following safety outcomes will be identified by ICD-10-CM billing codes (Appendix 5).

- Transfusion associated circulatory overload (TACO)
- Transfusion-related acute lung injury (TRALI)
- Anaphylactic reaction

---

a The following events were excluded because they are irrelevant for plasma transfusion or because there are no transfusion-specific billing codes. Transfusion-associated graft vs. host disease (TAGVHD) is associated with a cellular product. Delayed hemolytic transfusion reaction (DHTR) and delayed serologic transfusion reaction (DSTR) are associated with red cells containing products. Post transfusion purpura (PTP) is associated with platelets containing products. No transfusion specific billing codes exist for transfusion-associated dyspnea (TAD) allergic reaction and hypotensive transfusion reaction.

- Febrile non-hemolytic transfusion reaction
- Transfusion-transmitted infection
- Acute hemolytic transfusion reaction
- A composite outcome of thrombotic or thromboembolic complication including stroke, myocardial infarction, venous thromboembolism, deep vein thrombosis, and pulmonary embolism
- A composite outcome of cardiac arrhythmias including ventricular tachycardia, ventricular fibrillation, atrial arrhythmia, and cardiac arrest
- Effectiveness
  - Primary:
    - 28-day in-hospital mortality
  - Secondary:
    - Discharge alive
    - ICU transfer
    - Mechanical ventilation

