## **IV. STATISTICAL ANALYSIS PLAN**

### **All patients**

#### Descriptive Analyses

We will describe distribution of baseline covariates (Appendix 2), including demographics, comorbidities, concomitant medications, and severity measures of COVID-19 for the exposed and unexposed groups. The number of patients, mean, standard deviation, median, interquartile range, and range will be presented for continuous variables, and counts and percentages of patients in each category will be presented for categorical variables.

Given the modest sample size and rarity of the safety outcomes, we will explore the occurrence of safety outcomes, and present counts and percentages.

The crude incidence rates of death in the first 7, 14, 21, and 28 days after the index date will be estimated for the exposed and unexposed groups using the cohort before propensity score matching.

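### Six of the eight safety outcomes are transfusion reactions, so the unexposed percentage is near zero by definition and the comparison in primary objective (ii) does not measure plasma harm for them

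*Protocol*

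**What the plan says.** Section II.A of the protocol sets primary objective (ii): "To describe safety outcomes of interest in laboratory confirmed COVID-19 patients who received convalescent plasma compared with COVID-19 patients who did not receive" plasma. The objective is descriptive, but the comparator is part of it.

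Study Outcomes explains where the events come from: "Safety events related to plasma transfusion were selected from" a national hemovigilance surveillance protocol. It also says how they are found: "The following safety outcomes will be identified by ICD-10-CM billing codes", listed in Appendix 5. Six hemovigilance reactions follow, then two composites. One composite covers arrhythmias; the other is "A composite outcome of thrombotic or thromboembolic complication including stroke, myocardial infarction, venous thromboembolism, deep vein thrombosis, and pulmonary embolism".

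The footnote to that section says events were dropped because they are irrelevant to plasma "or because there are no transfusion-specific billing codes". It adds: "No transfusion specific billing codes exist for transfusion-associated dyspnea (TAD) allergic reaction and hypotensive transfusion reaction".

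Under Descriptive Analyses the plan is: "we will explore the occurrence of safety outcomes, and present counts and percentages". No test or effect estimate is planned for safety.

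On crossover, step 3 of the risk-set sampling states: "One patient could be sampled at maximum twice; first sampled into the unexposed group and later sampled into the exposed group". Cohort Sampling ends an unexposed patient's follow-up when plasma is given. The intent-to-treat analysis under Limitations does not. Neither place gives a rule for safety outcomes.

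**The concern.** A comparator is useful for safety when its percentage shows how often the event would occur without the treatment. The footnote's selection rule prevents that for the six reactions, because an event whose code names a transfusion cannot properly be recorded in a patient who had none. The clinical states behind the labels, such as fluid overload, lung injury and fever, can occur in hospitalized COVID-19 patients without plasma, but they would be coded differently and would not appear in the table.

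A table of some percentage against roughly zero, under an objective worded as a comparison, invites the reader to take the gap as excess harm from plasma. Much of that gap comes from the code definitions. The exposed percentage is not a clean plasma reaction rate either, because red cells, platelets or ordinary plasma can lead to the same codes. The protocol accepts elsewhere that the product matters: its footnote excludes some reactions because they belong to red cells or platelets.

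**Working it through.** The protocol gives no safety rate, so there is no figure to reproduce. The check is a count of codes, followed by arithmetic on labelled assumptions.

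**1. Codes for the six reactions (Appendix 5)**

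| Outcome | Codes | Presupposes transfusion or blood product? |
|---|---|---|
| TACO | E87.71 | yes |
| TRALI | J95.84 | yes |
| Anaphylactic reaction | T80.51XA | yes |
| Febrile non-hemolytic reaction | R50.84 | yes |
| Transfusion-transmitted infection | T80.22XA | yes |
| | T80.29XA | no: also covers other infusions and therapeutic injections |
| Acute hemolytic reaction | T80.910A, T80.A10A | yes, both |

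Six of eight outcomes are affected, through eight codes, of which seven presuppose a transfusion or blood product.

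**2. What the two percentages measure.** Let p be the plasma reaction rate and s the reaction rate among patients given another blood product. Let q1 and q0 be the shares of exposed and unexposed patients given such a product. For the seven codes:

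- unexposed percentage = q0 × s
- exposed percentage = p + q1 × s

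The unexposed percentage contains only use of, and reactions to, other products. If q0 = 0 it is zero. A ratio of the two therefore moves with co-transfusion while p stays fixed. With p = 1% and q1 = q0 (assumed):

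- q = 5%, s = 1%: 1.05% against 0.05%, ratio 21
- q = 10%, s = 2%: 1.2% against 0.2%, ratio 6
- q = 30%, s = 2%: 1.6% against 0.6%, ratio 2.7

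The difference, p + (q1 − q0) × s, equals p only if q1 = q0. Other blood products are neither a matching variable nor a propensity score covariate, so nothing in the plan secures that.

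**3. Share of exposed events not due to plasma.** Take 400 recipients (a 1:4 row of Table 1) and assume p = 1%, which gives 400 × 1% = 4 plasma events.

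- 5% also given another product, 1% of them reacting: 400 × 5% × 1% = 0.2; 0.2/4.2 = 5%
- 10% and 2%: 0.8 events; 0.8/4.8 = 17%; coded rate 4.8/400 = 1.2%
- 30% and 2%: 2.4 events; 2.4/6.4 = 38%

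None of these rates comes from the protocol. They show sensitivity and are not an estimate.

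**4. Crossover.** Follow-up of an unexposed patient ends at plasma administration in the main design, so a later reaction falls outside unexposed time. It could enter the unexposed count only if the intent-to-treat analysis is extended to safety, or if codes carry no usable date. The protocol does not say whether they are dated.

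**5. What a recipient-only report would deliver.** With zero events in n recipients, the upper limit of the exact two-sided 95% interval is 1 − 0.025^(1/n). That is 1.8% for n = 200 and 0.74% for n = 500, both group sizes in Table 1. These are usable statements about a reaction rate, and they need no comparator.

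**The case against.** The strongest reply is that the plan is modest. Objective (i) estimates a relative risk; objective (ii) only describes, and the analysis is counts and percentages for rare events. Time windows, code dating and co-transfusion rules can sit in a separate statistical analysis plan, and Appendix 4 is to record definitions and time points during abstraction. The unexposed count is also not worthless, since it shows reactions to other products. If their use were equal in the two groups, the simple difference would remove them.

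Much of this stands. Absent windows and dating rules are not in themselves a fault of this protocol, and an unexposed count correctly labelled is acceptable. What it does not answer is that the comparator is written into a primary objective and the outcome definitions into the protocol, and that together they give a column which is not a background rate.

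A reader might go further than the document supports in four ways:

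- *An unexposed patient can have these codes only through another blood product or later plasma.* T80.29XA breaks that rule, since any infusion or injection can lead to it.
- *Crossover patients' reactions are counted in both groups.* Step 3 does allow a patient in both groups, but censoring at plasma administration removes those events from unexposed time in the main design.
- *Attribution to plasma is impossible.* It is unplanned: the date and time of each plasma administration are captured.
- *The whole safety description is uninformative.* The two composites can occur in either group and can be compared, subject to confounding.

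**Conclusion.** The concern holds for six of the eight safety outcomes. For seven of their eight codes the unexposed percentage is close to zero by definition, which follows from the code descriptions and needs no assumption about rates. The exposed percentage may also contain reactions to other products. How much is unknown: the 5% to 38% range rests wholly on assumed rates. T80.29XA is a separate, smaller fault, because it would count infections after non-blood infusions as transfusion-transmitted. The effectiveness analyses are unaffected, and the plan itself draws no causal conclusion on safety. The change should be made because most outcomes under a primary objective do not answer it as written.

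**What to change.** Amend primary objective (ii), Study Outcomes and Descriptive Analyses as follows.

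- Report the six reactions as occurrence among all plasma recipients, with exact 95% confidence intervals. Count only events dated at or after a plasma administration and within a window that the protocol states.
- Show them with and without another blood product in that window, if the blood bank systems hold those records.
- Limit the exposed-versus-unexposed description to the thrombotic and arrhythmia composites. If an unexposed count is kept for the six, label it as reactions to other products and restrict it to time before crossover, in any intent-to-treat analysis as well.
- Remove T80.29XA or report it on its own line.

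The cost is one comparator column lost or relabelled, plus an extra query of SoftBank and SafeTrace. Data Sources names those systems only for convalescent plasma data, so it must be checked that they hold other issued products. Event dates must also be obtainable alongside the billing codes. If they are not, the report should say that timing relative to plasma could not be established.

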### B. EXPLORATORY OBJECTIVES

- (i) To estimate the relative risk of in-hospital mortality through 28 days among patients with HIV and laboratory confirmed COVID-19, who received convalescent plasma compared with those who did not receive convalescent plasma.
- (ii) To describe demographics, clinical characteristics, and outcomes of the population of COVID-19 patients treated concurrently with remdesivir and convalescent plasma.

## III. STUDY DESIGN

### Study Period

July 1, 2020 to October 25, 2020 (the date of data pull)

[figure not shown]
The start date is when all hospital sites started using the same ERH management system. The study period end date is October 25, 2020 with last convalescent plasma administration occurring 28 days prior on September 27, 2020.

### Cohort Sampling

This is a retrospective cohort study with risk-set sampling for exposure status of convalescent plasma using EHRs in the Baylor Scott & White Health (BSWH) healthcare delivery system. In brief, patients who received convalescent plasma will be matched to a similar population who did not receive convalescent plasma around the same time ( $\pm 2$  days) of transfusion across sites. The administration date of convalescent plasma for the treated population and the matched date for the untreated population are thereafter referred as the index date. The matching scheme for risk-set sampling is defined in step-by-

step points in the following paragraph. The follow-up for the matched cohort will start from the index date and continue until the end of the observation period. The observation period for this study is defined as at least 28 days from the index date. In other words, the index date must be at least 28 days prior to the date of data pull to allow for adequate follow-up and minimize selection bias from informative censoring due to death or discharge for palliative care. An unexposed patient at the index date could receive convalescent plasma during the follow-up and the follow-up will be censored at the administration date of convalescent plasma (Figure 1).

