#### Comparative Analyses

A Kaplan-Meier curve will be plotted using the propensity score matched cohorts. To control for measured confounding, patients will be sampled in risk sets with replacement and propensity score matched. Distribution of covariates between exposure groups before and after propensity score matching will be assessed to evaluate the balance of baseline covariates and potential residual confounding. Absolute standardized differences, the differences in means or proportions divided by the pooled standard deviation, will be computed for each covariate to check its distribution balance within exposure groups. Covariates with an absolute standard difference greater than 0.1 will be further controlled in the analyses by including specific variables in the Cox model.

The adjusted incidence rates of death in the first 7, 14, 21, and 28 days after the index date will be estimated for the exposed and unexposed groups using the propensity score-matched cohort.

For the primary outcome (28-day in-hospital mortality), a Cox proportional hazards regression will estimate hazards ratios (HRs) and 95% confidence intervals (CIs) using the propensity score-matched cohort. Patients will be followed from the index date until the earliest of the following: 1) death, 2) discharge alive, 3) day 28 since the index date, or 4) the date of unexposed patients who were administered COVID-19 convalescent plasma. Patients discharged alive will be censored at the discharge date. The proportional hazards assumption will be evaluated using Schoenfeld residuals test and visual inspection of log-log plots.

For the secondary outcome of discharge alive, we will not censor the follow-up at the date of in-hospital death but will censor at day 28 to account for this worst possible outcome and to account for the competing risk of in-hospital death. In other words, patients will be followed from the index date until the earliest of the following: 1) discharge alive, 2) day 28 since the index date, or 3) the date of unexposed patients who were administered COVID-19 convalescent plasma.

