### Sensitivity Analyses

- 1) To assess the COVID-19 cohort definition of hospital admission within ±14 days of laboratory confirmed COVID-19 diagnosis, we will further restrict the source population to those who were admitted into affiliated BSWH hospitals within ±7 days of laboratory confirmed COVID-19 diagnosis. This is because COVID-19 could progress quickly and patients could also transfer to hospitals outside of the network of BSWH with a large time window around COVID-19

confirmation resulting in potential residual confounding by severity and survivor bias by prior treatment

- 2) Instead of ending the observation period at 28 days since the index date, we will continue follow-up until the end of the study period, unless an outcome event occurs earlier. Patients will be followed from the index date until the earliest of the following: 1) death, 2) discharge alive, 3) the end of the study period, or 4) the date of unexposed patients who were administrated COVID-19 convalescent plasma.
- 3) Given that mortality data after hospital discharge is limited and that patients could be discharged for palliative care due to disease worsening, the outcome “discharge alive” will be considered a competing risk for 28-day in-hospital mortality. To account for competing risk of in-hospital death and discharge alive, sub-distribution hazard ratios will be estimated from the Fine-Gray model. Cumulative incidence function will be estimated by modeling the cause-specific hazard function of all causes.

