**VI. LIMITATIONS**

Unmeasured confounding

Given that patients were not randomly assigned to receive convalescent plasma, confounding by indication may not be fully accounted for using the available data elements in EHRs. Missing data and misclassification for covariates may result in residual confounding and biased risk estimates. For example, the convalescent plasma exposed group may appear to have a more favorable clinical outcome compared to the unexposed group, because the unexposed group had more severe disease to start with, and the two groups were not comparable at the index date. Alternatively, the exposed group may appear to have no favorable clinical outcomes or even worse outcomes, because patients in this group started with more severe disease at the index date.

Although risk-set sampling and propensity score matching are used to control measured confounding, EHRs are not able to fully capture all important prognostic factors related to outcomes of interest. To evaluate the possible impact of unmeasured confounding, we will consider exploring some of the methods listed below if feasible.

- Quantitative bias analyses
- Negative outcome controls
- E-values 
- Instrumental variables

Informative censoring

Treatment switches or hospital transfers during follow-up may be related to worsening of COVID-19. To evaluate this potential selection bias, we will use an intent-to-treat (ITT) analysis, whereby treatment switches will not censor the follow-up and instead fixed duration of follow-up will be used. Reasons for and where patients were transferred will be assessed according to exposure groups.

Effect modification by antibody titer

This observational study does not impose the inclusion criterion of seronegative for SARS-CoV-2 because testing antibody titers before administering convalescent plasma is not the present routine clinical practice at BSWH. Hence, individual antibody titers/humoral immunity in patients is not accounted for. The neutralizing capacity of convalescent plasma received by patients is not tested nor captured in the EHRs. In addition, the effective level of neutralizing titers inpatients who have received passive antibody therapies is also unknown. If a limited or no association between convalescent plasma and the clinical outcomes are observed, the results may not be interpreted as a true “no effect” of convalescent plasma due to the uncertainty of the titer values.

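### The primary Cox model censors unexposed patients at later plasma without adjustment; if worsening prompts switching the HR is biased against plasma, and Section IV omits the promised ITT check

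*Protocol*

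**What the plan says.** - **Censoring rule.** Cohort Sampling (Section III) allows an unexposed patient to receive plasma later, in which case "the follow-up will be censored at the administration date of convalescent plasma". Comparative Analyses (Section IV) makes this the fourth reason for ending follow-up for the primary outcome: "4) the date of unexposed patients who were administered COVID-19 convalescent plasma". The same rule applies to discharge alive, ICU transfer and mechanical ventilation.
- **Primary model.** "a Cox proportional hazards regression will estimate hazards ratios (HRs) and 95% confidence intervals (CIs) using the propensity score-matched cohort". The propensity covariates are defined at baseline only. No censoring weights or post-index covariates are stated.
- **Recognition of the problem.** Section VI, under Informative censoring: "Treatment switches or hospital transfers during follow-up may be related to worsening of COVID-19".
- **Promised check.** The same paragraph continues: "we will use an intent-to-treat (ITT) analysis, whereby treatment switches will not censor the follow-up and instead fixed duration of follow-up will be used".
- **Sensitivity list.** Section IV names three analyses: a ±7-day admission window, longer follow-up, and a Fine-Gray model for discharge. None lifts the switch censoring, and the second repeats it: "4) the date of unexposed patients who were administrated COVID-19 convalescent plasma".

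**The concern.** Only the unexposed group can be censored by switching. A Cox model is valid under such censoring if, given the covariates in the model, patients who switch have the same future hazard as those who stay. Matching at the index date cannot secure this, because the selection arises afterwards from how the illness develops. If clinicians give plasma to patients who are getting worse, the remaining unexposed patients are healthier than the group they represent and their death hazard is understated. The HR then rises even when plasma does nothing, or a real benefit is partly hidden.

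The analysis that would show whether this matters is promised in Section VI. It is missing from Section IV, which is headed as the statistical analysis plan and lists the sensitivity analyses.

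**Working it through.** **The plan's own figures.** The protocol gives no switching rate and no estimate of this bias. Its only related figures are in Table 1 (Section V). The first row (500 + 500, relative risk 0.71, survival 0.75) reproduces under Freedman's formula with relative risk read as a risk ratio:
- treated survival = 1 − 0.25 × 0.71 = 0.8225; HR = ln(0.8225)/ln(0.75) = 0.679
- expected deaths = 500 × 0.25 + 500 × 0.1775 = 213.75
- z = √213.75 × (1 − 0.679)/(1 + 0.679) − 1.96 = 0.83, so power is about 80%

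All 16 rows give 78.8-81.2% power. The sample size is not in question and serves only as a yardstick.

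**Model 1: daily two-state model, no plasma effect, perfect baseline matching.** Every input is an assumption:
- a stable patient deteriorates with probability 6% per day
- death is 0.6% per day if stable and 3.6% if deteriorated
- discharge is 10% per day if stable and 3% if deteriorated
- 28-day in-hospital mortality without switching is then about 18%

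With Y the number at risk and d the deaths on each day (1 exposed, 0 unexposed) and k unexposed per exposed patient, the Cox HR θ solves

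Σ [d1 − (d1 + k·d0) × θY1/(θY1 + kY0)] = 0.

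| Daily plasma probability, stable / deteriorated | Unexposed who switch | Cox HR, 1:1 | Cox HR, 1:4 |
|---|---|---|---|
| 0.3% / 2% | 8% | 1.03 | 1.03 |
| 0.5% / 3% | 12% | 1.05 | 1.05 |
| 1% / 5% | 18% | 1.08 | 1.08 |
| 2% / 10% | 28% | 1.16 | 1.17 |
| 2% / 20% | 33% | 1.37 | 1.42 |
| 3% / 3% (unrelated to worsening) | 22% | 1.00 | 1.00 |
| 3% / 1% (stable switch more) | 17% | 0.97 | 0.97 |

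The mechanism shows in the third row. After 14 days, 66% of exposed patients still at risk have deteriorated, against 57% of unexposed patients. Their average daily death probabilities are 0.34 × 0.6% + 0.66 × 3.6% = 2.58% and 0.43 × 0.6% + 0.57 × 3.6% = 2.31%, a ratio of about 1.1 although plasma has no effect.

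**Model 2: different assumptions, Cox fit at 1:4.** 25% 28-day mortality without plasma, worsening at 0.03 per day, death hazard 4 or 10 times higher after worsening, 5-30% switching, no discharge.

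| Plasma effect on the death hazard | Switching pattern | HR with no switching | Censored analysis | ITT |
|---|---|---|---|---|
| 1.0 | worsened switch 3-10 times as often | 1.00 | 1.01-1.17 | 1.00 |
| 1.0 | unrelated to worsening | 1.00 | 1.00 | 1.00 |
| 1.0 | worsened switch one third as often | 1.00 | 0.96-0.99 | 1.00 |
| 0.7 | worsened switch 3-10 times as often | 0.71-0.72 | 0.71-0.85 | 0.72-0.79 |

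The two models agree on direction. The last row shows that ITT removes the bias when plasma does nothing but is itself pulled toward 1 when plasma works.

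**The case against.** The strongest reply is that the protocol already knows of the problem. It has a heading for it, states why it would run an ITT analysis, and says it will do so, in firmer terms than it uses for the unmeasured-confounding methods just above. A separate analysis plan may hold the model details, and their absence here is no fault. This stands: the ITT analysis is a firm commitment made to evaluate this bias. What remains is that Section IV fixes the censoring rule, lists the sensitivity analyses without that one, and offers no analysis that adjusts for post-index severity.

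Four stronger readings are tempting and not supported:

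- **That the protocol says switching tracks worsening.** It says only that switches or transfers may be related to worsening. Neither direction nor frequency is documented, so bias against plasma is conditional.
- **That the bias is 1.07 to 1.70.** A crude ratio of deaths per person-day gives about that range in the first five scenarios of Model 1, but the plan uses a Cox HR. Hazard rises over time in that model, so shorter unexposed follow-up lowers the crude rate even when switching is uninformative: at 3% / 3% the crude ratio is 1.10 while the Cox HR is 1.00.
- **That fixed follow-up contradicts stopping at discharge.** For a 28-day in-hospital outcome, a patient discharged alive can be counted as an in-hospital survivor to day 28. The text leaves this open but does not contradict itself.
- **That the remedies are free.** Covariates are planned at baseline only, so weighting needs new extraction. ITT dilutes a real effect. Because a patient may be sampled first as unexposed and later as exposed, ITT would also count a switcher's post-plasma time in both groups.

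**Conclusion.** The concern holds in conditional form. The primary HR may be biased, upward and against plasma if worsening prompts switching. There is no bias if the two are unrelated, and the bias is downward if stable patients switch more. Baseline matching does not protect against it, and no analysis in Section IV would reveal it.

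The size rests on the assumed models above, not on the documents. With no true effect, the bias is about 3-8% at 8-18% switching and 16-17% at 28%. It reaches about 40% only at 33% switching with a tenfold difference. A study sized for a relative risk of 0.7 could absorb the small values. The upper part of the range (0.85 where the no-switching HR is 0.72, in Model 2) could hide an effect it was designed to find. This should be corrected before analysis, but it does not invalidate the design.

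**What to change.** 1. Add to Section IV an analysis of the 28-day primary outcome weighted by the stabilised inverse probability of remaining free of plasma, estimated from post-index oxygen level, laboratory values, days since admission and site. Report it beside the unweighted HR.
2. List the promised ITT analysis in Section IV for the same outcome. Count patients discharged alive as in-hospital survivors to day 28, and note that it dilutes a real effect.
3. Report the number and timing of switches among unexposed patients, which shows how much room there is for bias.
4. Use a robust variance clustered on patient, because a switcher can appear in both groups.

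**Cost.** Post-index values must be extracted and validated for variables now planned only at baseline, with the chart check that Data Sources requires. Weighted intervals will be somewhat wider, and the weights correct only for severity that is measured. The ITT run and the switch counts add little, since the first is already promised and the second uses dates the censoring rule already needs.
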